5.2 Analyses and reporting

All final, planned, analyses identified in the protocol and in this SAP will be performed only after the last patient has completed the study.

Any post-hoc analyses included in the CSR, which were not identified in this SAP, will be clearly identified as such in the relevant section of the CSR.

For each patient in the study, all the associated safety and efficacy data in the SOBI003-001 study will be pooled and presented together with the SOBI003-002 study. Thus the SOBI003-001 study and the SOBI003-002 study are considered as a single, unified entity.

6 Estimands

There will be a de facto estimand in the study, which is the primary estimand for the evaluation of efficacy. The estimand is the change in

- cognitive decline in all the patients from the population captured by the inclusion and exclusion criteria (see Section 4.2.1 and Section 4.2.2) and the part of the NH population with a rapid progressive disease having a baseline age of 12 to 72 months, irrespectively of other medications used and adherence to treatment, and estimated by a repeated measures model of the change from baseline in DQ as described in Section 14.1.

- decline in HS levels in CSF in all the patients from the population captured by the inclusion and exclusion criteria (see Section 4.2.1 and Section 4.2.2) irrespectively of other medications used and adherence to treatment, and estimated by a repeated measures model of the change from baseline in HS as described in Section 14.1.

To address foreseeable inter-current events, such as drop-outs, all missing values will be imputed (see Section 14.1) in accordance with the treatment policy principle. A sensitivity analysis will be performed where no imputations are performed, but all values are used: If a patient has a missing value in any assessment, then the same patient's non-missing scores will be used in the repeated measures model. The repeated measures model (see Section 14.1) handles missing values based on the missing at random (MAR) assumption. One further sensitivity analysis for DQ will address this assumption based on zero imputations (see Section 14.1.1), the rationale being that the patients not assessed are those expected to have a severe DQ decline. Other sensitivity analyses for this purpose will be tipping point analyses, see Section 14.1.1.

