9.1 Handling of missing data

All missing DQ values and HS in CSF values will be imputed. The procedure is fully described in Section 14.1. A sensitivity analysis will be performed where no imputations are performed, but all values are used: If a patient has a missing DQ score in any assessment, then the same patient's non-missing scores will be used in the repeated measures model. The repeated measures model (see Section 14.1) handles missing values based on the MAR assumption. One further sensitivity analysis will address this assumption based on zero imputations (see Section 14.1.1), the rationale being that the patients not assessed are those expected to have a severe DQ decline. Another sensitivity analysis for this purpose will be a tipping point analysis, see Section 14.1.1.

If an adverse event (AE) has a completely missing onset date, then the AE will be considered a TEAE, unless the (partial) stop date indicates differently. A medication with a completely missing start date is considered a prior medication. A medication with a completely missing stop date is considered a concomitant medication. If an AE or a medication has a partial missing start or stop date, the following rules will be used to impute the date. The imputed date will be used to determine whether it is a TEAE for adverse event, or a prior or concomitant medication.

Table 1 Partial date derivation

Partial Missing Start or Stop Date	Derived Start Date	Derived Stop Date
Missing month and day, and the year is present	January 1 st of that year or first dose date if the year is the same as the year of first dose date	December 31 st of that year

Partial Missing Start or Stop Date	Derived Start Date	Derived Stop Date
Missing day, but year and month are present	First day of that month or first dose date if the year and month are the same as the year and month of first dose date	Last day of that month
Missing month, but year and day are present	Missing month derived as January or same as first dose month if the year is the same as the year of first dose	Missing month derived as December

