15.2 Adverse events

An adverse event (AE) is defined as any untoward medical occurrence, including a clinically significant laboratory finding, symptom, or disease in a patient enrolled into this study regardless of its causal relationship to study drug.

A treatment-emergent AE (TEAE) is defined as any event not present before exposure to study drug or any event already present that worsens in either severity or frequency after start of treatment.

Adverse events will be coded using the latest version of Medical Dictionary for Regulatory Activities (MedDRA).

An overview table will present the following information.

- Number and percentage of patients reporting TEAEs
- Number and percentage of patients reporting serious TEAEs
- Number and percentage of patients reporting TEAEs leading to death
- Number and percentage of patients reporting TEAEs leading to study discontinuation
- Number and percentage of patients reporting TEAEs related to study drug

The number of events will also be displayed in this summary table.

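### SAP 9.1 imputes a partly missing AE onset without checking the stop date, so an event that ended before the first dose can be counted as treatment-emergent with an onset after its own end

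*SAP*

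**What the plan says.** SAP 9.1 treats two situations differently.

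- **Onset completely missing:** "then the AE will be considered a TEAE, unless the (partial) stop date indicates differently". The stop date can overrule the default.
- **Onset partly missing:** Table 1 derives a start date.
  - Row one (month and day missing): "January 1 st of that year or first dose date if the year is the same as the year of first dose date".
  - Row two (day missing): "First day of that month or first dose date if the year and month are the same as the year and month" of the first dose.
  - Row three (month missing): January, or the first dose month if the year matches.

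No row places a condition on the stop date. On how the result is used, the section says: "The imputed date will be used to determine whether it is a TEAE for adverse event". The same table and sentence also serve medications (prior or concomitant).

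The TEAE definition in SAP 15.2 reads: "any event not present before exposure to study drug or any event already present that worsens in either severity or frequency after start of treatment". Protocol 7.5.4.1.1 likewise counts onset or worsening from the first dose of study drug. SAP 5.2 says that each patient's safety and efficacy data from the FIH study "will be pooled and presented together with the SOBI003-002 study".

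**The concern.** Moving a partial onset to the first dose date is a common conservative default for events whose timing is unknown. Here it also reaches events whose timing is known well enough: if the recorded stop lies before the first dose, the event was over before exposure whatever the missing day or month. Such an event meets neither limb of the SAP 15.2 definition. It was present before exposure, and it cannot have worsened after treatment began.

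The rule is also inconsistent within its own section. A record with no onset date at all is protected by its stop date, while a record with a known year or month is not. The better-documented event gets the worse classification. The exception for completely missing onsets shows that the authors expected AEs that ended before the first dose.

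TEAEs are part of the primary endpoint (protocol 6.1.1, SAP 3.5.1). The false onset would also carry into the per-patient figures in SAP 15.2.1. In rows one and two, a pre-treatment event would be drawn on the exposure curve at the date of the first infusion.

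**Working it through.** The plan states no figure on this point to reproduce. The check applies Table 1 literally to test dates.

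**Inputs**
- Start and stop derivations: SAP 9.1 Table 1.
- TEAE if the imputed start is on or after the first dose date: SAP 9.1 read with SAP 15.2.
- First dose date: 15 June 2019, assumed for illustration, since the documents give no dates.
- Planned number of patients: 9 to 12 (protocol synopsis).

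**Results**

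| Row | Recorded onset | Recorded stop | Derived onset | Stop used | Onset minus stop | Class |
|---|---|---|---|---|---|---|
| Two | June 2019 | 5 June 2019 | 15 June | 5 June | +10 days | TEAE |
| Two | June 2019 | June 2019 | 15 June | 30 June | none | TEAE, no contradiction |
| One | 2019 | 10 March 2019 | 15 June | 10 March | 21+30+31+15 = +97 days | TEAE |
| One | 2019 | March 2019 | 15 June | 31 March | 30+31+15 = +76 days | TEAE |
| One | 2019 | 2019 | 15 June | 31 December | none | TEAE, no contradiction |
| Three | day 20, 2019 | 25 March 2019 | 20 June | 25 March | 6+30+31+20 = +87 days | TEAE |
| Three | day 5, 2019 | 10 March 2019 | 5 June | 10 March | 21+30+31+5 = +87 days | Not a TEAE, but onset after end |

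The result does not depend on the chosen stop date. In row two, all 14 complete stop dates from 1 to 14 June give a TEAE with onset after end. In row one, so do all 165 complete stop dates from 1 January to 14 June (31+28+31+30+31+14 = 165). In row three, the misclassification also needs the recorded day to fall on or after the day of the first dose.

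**Comparison within SAP 9.1.** Take the first line of the table and delete the onset month and year, so that the onset is completely missing. The stop of 5 June now shows that the event ended before treatment, and the AE is not a TEAE. Removing information corrects the classification.

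**Conditions for the error.** (a) The known part of the onset matches the first dose (year, or year and month). (b) The recorded or derived stop is before the first dose. Table 1 derives stops as late as the recorded parts allow, so a derived stop before the first dose means that the event was certainly over.

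**Size in a table row.** One patient out of 12 is 1/12 = 8.3%, and one out of 9 is 1/9 = 11.1%. The SAP 15.2 tables count patients with at least one event, so the percentage moves only if that child has no other event in the row. Otherwise only the event count rises, by one.

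**Medications.** SAP 12 calls a drug prior if it ended before Day 1, and concomitant if, among other conditions, it started on or after Day 1. A derived start at the first dose date with an earlier recorded stop meets both definitions, if Day 1 is the first-dose day.

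**The case against.** The strongest reply is that SAP 9.1 does not say that the imputed date alone decides. Read with the stop-date exception in the same paragraph and the definition in SAP 15.2, a sensible programmer would exclude an event recorded as over before the first dose. That may happen in practice. But the exception is written only for completely missing onsets, Table 1 is explicit, and no other section caps the derived start. Two programmers could produce different TEAE counts, and the one who follows the text would be wrong.

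A second reply concerns reach, and much of it stands. Every extension patient has already had 24 weeks of treatment. With the studies pooled, first dose most naturally means the first FIH dose, so only FIH events before that dose are exposed, and these documents do not say when FIH AE recording began. If first dose meant the Week 25 infusion, events since the last FIH visit began on treatment, and calling them treatment-emergent would not be an error under the pooled definition.

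A third reply is that the error is conservative and the safety summaries are descriptive. Both are true. No hypothesis test is affected.

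A reader might also infer more than the documents support:
- **That these events are attributed to SOBI003.** TEAE status is about timing. Causality is assessed and tabulated separately (protocol 7.5.4.1.3, SAP 15.2.5), and an event that ended before any dose would not fit the protocol's definition of related.
- **That complications of venous port insertion are caught.** Protocol 5.2 says that the port is added as part of the FIH study, but not that this happens before the first dose with AE recording open.
- **That medication listings will show negative durations.** SAP 9.1 states only that imputed dates are used for classification, not that they feed the duration of use.

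**Conclusion.** Wrong as written, low severity. Applied literally, Table 1 classifies an AE that ended before the first dose as a TEAE with an onset after its end. This happens always in rows one and two once the two conditions are met, and in row three when the recorded day is on or after the first-dose day. It conflicts with SAP 15.2, protocol 7.5.4.1.1 and the logic of SAP 9.1 itself.

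The number of affected events cannot be derived and is probably small. The 8 to 11 percentage points are a ceiling per affected child and row, not a typical effect. The direction is an over-count. The conclusion that any event is affected assumes that the FIH study recorded AEs before its first dose. The fault in the rule does not depend on that assumption.

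**What to change.** Add to SAP 9.1, under Table 1 and for all three rows:

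> If the recorded or derived stop date is before the first dose date, the AE is not a TEAE (and the medication is prior). A derived start date may not be later than the stop date; in that case use the earliest date consistent with the recorded parts.

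In the examples above, the derived onsets become 1 June (row two, stop 5 June), 1 January (row one, stops in March), and 20 January and 5 January (row three). None of these events is then a TEAE. Events whose stop falls on or after the first dose, or is too incomplete to tell, keep the present default, so the conservative intent is preserved.

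The SAP should also state that first dose date, in Table 1, means the first dose in the FIH study, if that is what is intended under pooling.

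The cost is a short addition to the SAP and one programming condition, to be made before database lock. No data collection changes.

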##### 7.5.4.1.2 Adverse event reporting period

The period for recording AE, including SAEs, on the CRF begins Day 1 upon signing of the study ICF on Week 25 and ends at Day 8 of Week 104 (End of Study). This includes all events observed/diagnosed or reported since the last visit of the FIH study ([SOBI003-001](#)) (Week 24 / End of study).

In addition, SAEs should be reported, from the time the ICF is signed until 28 days past the last dose of IMP, unless the patient will continue SOBI003 treatment in a Sobi-sponsored extension study starting in direct connection to the study, collecting these events.

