3.5 Study endpoints

3.5.1 Primary endpoint

The primary endpoint to evaluate the safety and tolerability of SOBI003 is:

- Treatment Emergent Adverse Events (TEAEs) and Serious Adverse Events (SAEs)

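### The rule for a missing month in SAP Table 1 has no floor at the first dose date, so an on-treatment adverse event can be dated before treatment and lost from the TEAE counts

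*SAP*

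**What the plan says.** Table 1 in SAP 9.1 has three start-date rows.

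- **Month and day missing:** "January 1 st of that year or first dose date if the year is the same as the year of first dose date".
- **Day missing:** "First day of that month or first dose date if the year and month are the same" as those of the first dose.
- **Month missing, day and year known:** "Missing month derived as January or same as first dose month if the year is the same as the year of first dose".

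The text above the table says what the result is for: "The imputed date will be used to determine whether it is a TEAE for adverse event, or a prior or concomitant medication". A separate sentence covers an event with no onset date at all: "If an adverse event (AE) has a completely missing onset date, then the AE will be considered a TEAE", with an exception if the stop date points the other way. TEAEs and SAEs together form the primary endpoint (SAP 3.5.1).

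Table 1 does not say which first dose it means. SAP 5.2 treats SOBI003-001 and SOBI003-002 as one study, which suggests the first dose in SOBI003-001, but that is an inference. On recording in the extension, protocol 7.5.4.1.2 says: "This includes all events observed/diagnosed or reported since the last visit of the FIH study".

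**The concern.** Rows one and two keep an ambiguous event on the treatment side by replacing the whole date with the first dose date. Row three replaces only the month. If the recorded day is earlier than the day of the first dose, the derived onset falls before treatment, although the true onset may be months into it. No other passage in the SAP or protocol adds a floor or a default to TEAE for partial dates.

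The error runs one way: it can remove events from the TEAE counts. With 9 to 12 children, one child is 1/12 = 8.3 to 1/9 = 11.1 percentage points of an incidence. No reason is given for treating this row differently, so it reads as an omission.

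**Working it through.** The plan states no figure on this point, so there is nothing to reproduce. The check applies the rows as written.

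**Example.** First dose 20 March; true onset 10 August of the same year; month not recorded. Row three gives 10 March, ten days before the first dose, so the event is not a TEAE. With a floor it becomes 20 March and is a TEAE.

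**Share for one first-dose date.** Let the first dose fall on day d of month m, and let N be the number of days from then to 31 December inclusive. For first doses from February on, where every later month has at least 30 days, each later month contributes d − 1 backdated days:

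share = (12 − m)(d − 1) / N

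| First dose | Backdated days | N | Share |
|---|---|---|---|
| 1 March | 9 × 0 = 0 | 306 | 0% |
| 10 March | 9 × 9 = 81 | 297 | 27.3% |
| 20 March | 9 × 19 = 171 | 287 | 59.6% |
| 31 March | 9 × 30 = 270 | 276 | 97.8% |
| any day in December | 0 | – | 0% |

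**Average over first-dose dates.** Assumptions, not from the documents: the first dose is uniform over a 365-day year, and onset is uniform over 728 days (104 weeks) of treatment.

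- *First-dose year:* there are 365 × 366 / 2 = 66,795 pairs of first-dose date and onset. Direct enumeration finds 29,277 dated before treatment: 29,277 / 66,795 = 43.8%.
- *All 104 weeks:* there are 365 × 728 = 265,720 pairs. In later years the month becomes January, which is always after the first dose, so the count stays at 29,277: 29,277 / 265,720 = 11.0%.
- *Onset in the extension,* taken as day 168 (24 × 7) onward, with the first dose in SOBI003-001 as reference: there are 365 × 560 = 204,400 pairs. Onset falls in the first-dose year only if the first dose was on or before day 365 − 168 = 197 (16 July), which gives 197 × 198 / 2 = 19,503 pairs, or 9.5%. Of these, 43.7% are backdated: 0.0954 × 0.437 = 4.2%.
- *Rows one and two:* 0 backdated in the same enumeration.
- *Row three with the floor:* 0 backdated.

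All these are shares of events that lack only the month, not of all adverse events.

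**Side finding.** Row three can also produce a date that does not exist, such as day 31 in a 30-day first-dose month: 1,088 / 66,795 = 1.6% of first-dose-year cases. Table 1 has no rule for this.

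**The case against.** The strongest reply is that the trigger hardly ever occurs. Events are captured continuously with weekly infusion contacts, entered in an electronic CRF and checked against source. A known day and year with an unknown month should be very unusual. This stands, and it is why the point is minor. The documents give no frequency.

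Several stronger readings are tempting, and the documents do not support them.

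- *The event vanishes from the primary endpoint.* Only the TEAE part is affected. SAP 15.2.2 summarises all SAEs, SAP 9 lists all data, and worsening after the start of treatment still qualifies under SAP 15.2.
- *Row three contradicts the rule for a completely missing onset date.* That rule covers a different case and has its own stop-date exception. The rules are uneven, not contradictory.
- *Every row can pull an extension event back some 24 weeks to the first dose in SOBI003-001.* Row two needs the same month and year as the first dose, which an event 24 weeks later cannot have. Rows one and three can do it, if that first dose is meant, but row one leaves the event a TEAE.
- *The chance is (d − 1)/30, on average 14.5/30 = 48%.* This shortcut ignores that an on-treatment onset in the first-dose month cannot be backdated.
- *Events are misplaced in the tables by ADA status and titer.* SAP 9.1 assigns the derived date to TEAE and medication status only. Whether it also feeds those tables is not stated.

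**Conclusion.** The defect holds on the text. Followed as written, row three can class an on-treatment event as pre-treatment and remove it from the TEAE counts; rows one and two cannot. Both conditions are needed: the event falls in the calendar year of the first dose, and its recorded day is earlier than the first-dose day.

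Among month-only-missing events, the affected share is about 44% in the first-dose year, about 11% over 104 weeks and about 4% for onsets in the extension. These rest on uniform dates, and the last also on reading the first dose as that in SOBI003-001. The number of events at stake is probably very small. This is a minor correction to make before database lock, and it does not threaten the safety analysis as a whole.

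**What to change.** In SAP 9.1, Table 1:

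1. **Row three.** When the year equals the first-dose year, set the start date to the later of the derived date and the first dose date, unless the stop date shows that the event ended before the first dose. The year condition matters: without it, an event from an earlier year would be moved to the first dose and become a TEAE. The stop-date check prevents a start after the stop.
2. **Reference dose.** State which first dose is meant. If it is the first dose in SOBI003-001, do not date a new event first recorded in SOBI003-002 before the last SOBI003-001 visit (Week 24). A floor at Week 25 would not fit, because protocol 7.5.4.1.2 counts events since that last visit.
3. **Impossible dates.** Add a rule for a derived date that does not exist.

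The cost is a few lines of SAP wording and the matching code. No new data are needed.

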9.2 Multicenter studies

In order to examine the uniformity of the treatment effect across centers, additional statistical analyses will be performed on the DQ endpoint, consisting of descriptive, summary statistics presented by center in the treatment group.

9.3 Derived and computed variables

Scores (AEq and DQ) for neurocognitive development

Neurocognition is assessed at Weeks 52 and 104, and during Early Termination, by use of the neurocognition domain of the BSID-III and/or the KABC-II Nonverbal Index (NVI).

The selection of neurocognitive assessment method is done at the baseline assessment of the FIH study ([SOBI003-001](#)) based on the algorithm presented in **Error! Reference source not found.** The neurocognitive test(s) applied in the FIH study should also be used in the extension study.

Table 2 Selection of neurocognitive assessment method

Chronological age at the assessment time point	Development age-equivalence as established by VABS-II adaptive behavior composite	Neurocognitive test to apply
<42 months	Any age-equivalence	BSID-III
≥42 months	<36 months	BSID-III
≥42 months	36 to 42 months	BSID-III + KABC-II*
≥42 months	>42 months	KABC-II

* The BSID-III should be administered first, and there should be at least 2 days until the KABC-II assessment in order to reduce KABC-II outcome bias of patient tiredness.

The neurocognitive developmental age (months) is derived on the basis of the BSID-III cognitive total raw score and BSID-III age-normative data.

The neurocognitive developmental age (months) is derived from the mean AEq scores on the NVI of the KABC-II, where an AEq scores is the average score for a particular age.

Development Quotient

DQ is calculated as the AEq for cognitive development divided by the chronological age of the child multiplied with 100, i.e.

$$DQ = 100 * AEq / Age$$

For patients completing an assessment of both BSID-III and KABC-II, the BSID-III score will be used as a basis for calculating the DQ of neurocognitive development at baseline. A calibration of overlapping AEq scores between BDID-III and KABC-II will be done to assess if a patient outgrows the BSID-III test during the duration of the study. If confirmed, assessments of KABC-II will form the basis for calculating DQ of neurocognitive development for remaining study assessments.

10 Patient disposition

The following patient disposition details will be summarized and will include the number and percentage of patients:

- Included in the each study population (Safety analysis set, efficacy analysis set, immunogenicity analysis set, PK analysis set and PD analysis set)
- Completed the study
- Prematurely withdrew (including a breakdown of the primary reasons for withdrawal)

These data will be listed. Individual reasons for withdrawal and protocol deviations will be presented in listings for all randomised patients.

11 Demographics and baseline characteristics

